9.5. Pharmacokinetics and Immunogenicity

Pharmacokinetics/immunogenicity samples will no longer be collected in this study, therefore this section is no longer applicable.

Serum samples from venous blood collections will be used to evaluate the pharmacokinetics and immunogenicity (generation of anti-drug antibodies) of atezolizumab and daratumumab. Serum collected for pharmacokinetic and immunogenicity analyses may additionally be used to evaluate safety and efficacy questions, drug characteristics, or certain biomarkers for future research. Genetic analyses will not be performed on these serum samples. Subject confidentiality will be maintained.

9.5.1. Evaluations

Samples will be collected for measurement of serum concentrations of atezolizumab and daratumumab and the assessment of anti-atezolizumab and anti-daratumumab antibodies (immunogenicity). Serum samples should be collected at the final visit from subjects who are discontinued from treatment or withdrawn from the study. Subjects who discontinue treatment will also be asked to return for immunogenicity evaluation during the Follow-up Phase. These samples will be tested by the Sponsor or Sponsor's designee.

The exact dates and times of blood sampling must be recorded. Refer to the Laboratory Manual for sample collection requirements. Collected samples must be stored under the specified and controlled conditions for the temperatures indicated in the Laboratory Manual. Additional information about the collection, handling, and shipment of biological samples can be found in the Laboratory Manual.

9.5.2. Analytical Procedures

Serum samples will be analyzed to determine concentrations of daratumumab, concentrations of atezolizumab, or the generation of antibodies to daratumumab and atezolizumab using validated immunoassay methods.

All samples collected for detection of anti-atezolizumab and daratumumab antibodies will also be evaluated for serum concentration to enable interpretation of the antibody data. For the atezolizumab and daratumumab immunogenicity assessments, serum samples will be screened for antibodies binding to atezolizumab or daratumumab and serum titer will also be determined from confirmed positive samples. Other immunogenicity analyses (eg, assessment of neutralizing capabilities) may be performed to further characterize the immune responses that are generated. Neutralizing antibody assessments may also be performed to further characterize immune responses that are generated.

9.5.3. Pharmacokinetic Parameters

The PK parameters are defined as:

C_{\max} = Maximum observed concentration

C_{\min} = Minimum observed concentration

For both atezolizumab and daratumumab, the PK evaluations include C_{\min} and C_{\max} . If sufficient data are available, other PK parameters may be calculated. The C_{\min} and C_{\max} will be summarized by descriptive statistical method for Arm A and Arm B. If there are sufficient data, then a population PK analysis of serum concentration-time data of daratumumab and atezolizumab may be performed and may include data from other clinical studies. If performed, details will be provided in a population-PK analysis plan and the results of the analysis will be presented in a separate report.

9.5.4. Immunogenicity Assessments

When both serum concentration and immunogenicity analyses are specified, they will be performed on aliquots from the same blood draw and no additional sampling is required.

No unscheduled samples need to be collected for IRRs associated with the first administration of daratumumab. Daratumumab serum concentration will also be determined from the daratumumab IRR sample for interpreting immunogenicity data. If the IRR results in treatment discontinuation, then subjects should undergo all scheduled safety and efficacy evaluations. Procedures for sample collection, preparation, identification, storage, and shipment will be provided in the Laboratory Manual or equivalent document.

Subjects who discontinue treatment or withdraw from the study before confirmation of PD should have samples collected at the time of early discontinuation. Subjects who discontinue treatment will also be asked to return for immunogenicity evaluation during the Follow-up Phase.

9.6. Biomarker Assessments

Biomarker samples will no longer be collected in this study.

In this study, mandatory archival or fresh tumor specimens from subjects at Screening will be evaluated for expression of PD-L1⁺, CD38⁺, [REDACTED]

Published results suggest that the expression of PD-L1 in tumors correlates with response to anti-PD-L1 therapy (Horn 2015; Spira 2015).^{23,45} Evaluation of CD38⁺ expression will be performed to determine if elevated expression of CD38⁺ correlates with responses to daratumumab therapy.

Fresh biopsies at Cycle 3 and at progressive disease are mandatory, if clinically feasible, to evaluate biomarkers related to the clinical benefit of atezolizumab + daratumumab. Additionally, if a biopsy is taken at any other time while a subject is on study, a sample is also requested for biomarker analysis. Evaluation of biopsies by IHC and IF may include PD-L1 and CD38 expression in addition to other markers and cell populations [REDACTED] [REDACTED] [REDACTED] [REDACTED] to identify changes in inflammatory populations in response to treatment. Collection of a tumor biopsy, at the time of radiographic progression will be evaluated for immune infiltrate, PD-L1, and CD38 expression by IHC and is required in order to distinguish pseudoprogression/tumor-immune infiltration from true progression. Anti-tumor immune responses such as those potentially associated with atezolizumab + daratumumab may result in objective responses that are preceded by initial apparent radiological progression as a result of robust tumor-immune infiltration with a concomitant increase in tumor size in 8 to 10% of patients treated with PD-1 inhibitors (Dronca 2016).¹³ DNA or RNA extraction may be performed to enable next-generation sequencing (NGS) to identify biomarkers associated with disease progression or acquired resistance to atezolizumab + daratumumab and to increase understanding of disease pathobiology.

Evaluation of blood biomarkers may provide evidence for biomarkers of biologic activity of atezolizumab + daratumumab in subjects with NSCLC. Flow cytometry will be performed to immunophenotype [REDACTED] [REDACTED] [REDACTED] [REDACTED] [REDACTED] response to treatment. These samples may be used to evaluate specific subsets of immune cells [REDACTED] by CyTOF. Proteomic analysis may also be used to evaluate potential biomarkers of response and resistance.

9.6.1. Tumor Tissue Samples

As of 25 May 2018, scheduled tumor biopsies are no longer required. However, if a subject has an unscheduled tumor biopsy, tissue samples may be submitted as per protocol.

Archival and freshly collected tumor tissue samples for screening

Tumor tissue should be of good quality based on total and viable tumor content (sites will be informed if the quality of the submitted specimen is inadequate to determine tumor PD-L1 status). An archival tumor specimen can be submitted if available. Archival tumor biopsies are acceptable at baseline as long as the biopsy was collected after completion of the most recent prior therapy and is less than one year old. If an archival specimen is not available, the subject may still be eligible, with the assumption that the subject is willing to consent to and undergo a pretreatment biopsy or resection of the tumor. For subjects enrolled in the crossover arm, if a biopsy was taken at the time of disease progression while enrolled in Arm A of this protocol, a new biopsy is not required at Cycle 1X Day 1 predose.

For freshly collected biopsy specimens, acceptable samples include:

- Core needle biopsy sample collection for deep tumor tissue: At least 3 cores, embedded into a single paraffin block, should be submitted for evaluation.
- Excisional, incisional, punch, or forceps biopsy sample collection for cutaneous, subcutaneous, or mucosal lesions
- Fine-needle aspiration, brushing, cell pellets (eg, from pleural effusion), and lavage samples are not acceptable.

For archival samples, the remaining tumor tissue block for all subjects enrolled will be returned to the site upon request or 18 months after final closure of the study database, whichever is sooner. Tissue samples from subjects who are deemed ineligible to enroll in the study will be returned promptly after eligibility determination.

Tumor samples at Cycle 3 and at the time of confirmed radiographic progression

Subjects in all treatment arms will undergo a tumor biopsy to obtain a mandatory tumor sample, unless not clinically feasible, at Cycle 3, Cycle 3X, and at the time of radiographic disease progression.

Note: The Cycle 3 biopsy may be collected within 7 days prior to or up to 21 days after the Cycle 3 Day 1 dose but must be done prior to Cycle 4 Day 1. In addition, this biopsy must be performed following the first radiologic tumor assessment.

Acceptable samples include:

- Core needle biopsy sample collection for deep tumor tissue; at least three cores, embedded into a single paraffin block, should be submitted for evaluation.
- Excisional, incisional, punch, or forceps biopsy sample collection for cutaneous, subcutaneous, or mucosal lesions

Tumor tissue resection

The status of immune-related, tumor type-related, and other exploratory biomarkers (including, but not limited to, T-cell markers and non-inherited biomarkers identified through NGS on extracted DNA or RNA) in tumor tissue samples may be evaluated.

9.6.2. Biomarker Assays in Blood Samples

Blood samples will be obtained for biomarker evaluation (including but not limited to biomarkers that are related to NSCLC or tumor immune biology) from all eligible subjects. Samples will be processed to obtain plasma and serum for the determination of changes in blood-based biomarkers. Whole blood samples may be processed to obtain their derivatives (eg, RNA and DNA) and evaluated for immune-related, tumor type-related, and other exploratory biomarkers (eg, alterations in gene expression or clonal T-cell expansion). Also, based on emerging scientific evidence, the Sponsor may request additional blood samples for biomarker evaluation. In this case, such analyses will be limited to research related to the study drug(s) or diseases being investigated.

Stopping Analysis

Biomarker analyses are dependent upon the availability of appropriate biomarker assays and clinical response rates. Biomarker analysis may be deferred or not performed, if during or at the end of the study, it becomes clear that the analysis will not have sufficient scientific value for biomarker evaluation, or if there are not enough samples or responders to allow for adequate biomarker evaluation. In the event the study is terminated early or shows poor clinical efficacy, completion of biomarker assessments is based on justification and intended utility of the data.

Additional Collections

If it is determined at any time before study completion that additional material is needed from a FFPE tumor sample for the successful completion of the protocol-specified analyses, the Sponsor may request that additional material be retrieved from existing samples. Also, based on emerging scientific evidence, the Sponsor may request additional material from previously collected tumor samples during or after study completion for a retrospective analysis. In this case, such analyses would be specific to research related to the study drug(s) or diseases being investigated.

9.7. Safety Evaluations

Beginning with the implementation of Amendment 7, safety evaluations will be performed by the investigator according to local regulatory approvals and standard of care guidelines.^{50,51} These data will no longer be collected by the Sponsor with the exception of serious adverse events that are to be reported and entered in the Sponsor safety repository.

Safety will be assessed by the incidence and severity of adverse events, laboratory test results, ECGs, vital sign measurements, physical examination findings, ECOG performance status score, and other evaluations as described in the Time and Events Schedule (Table 1). Toxicities will be graded according to the NCI-CTCAE Version 4.03. Any clinically relevant changes occurring during the study must be recorded on the Adverse Event section of the CRF. Any clinically significant abnormalities persisting at the end of the study/early withdrawal will be followed by the investigator until resolution or until a clinically stable endpoint is reached.

Based on the previous human experience with daratumumab, in vitro studies, and animal toxicological findings, infusion-related reactions/allergic reactions, hemolysis, and thrombocytopenia will be closely monitored. As daratumumab and atezolizumab are both

biologic agents, immunogenicity also will be monitored. Any of the safety monitoring assessments may be performed more frequently, and adverse events should be evaluated by the investigator according to the standard practice, if clinically indicated.

Adverse Events

Adverse events will be reported by the subject (or, when appropriate, by a caregiver, surrogate, or the subject's legally acceptable representative) for the duration of the study. Adverse events will be followed by the investigator as specified in Section 12, Adverse Event Reporting.

Clinical Laboratory Tests

Blood samples for clinical laboratory evaluation will be collected. The investigator must review the laboratory results, document this review, and record any clinically relevant changes occurring during the study in the adverse event section of the CRF. The laboratory reports must be filed with the source documents. The following tests will be performed by the local laboratory, unless otherwise specified:

Hematology	
– Hemoglobin	– White blood cell (WBC) – Absolute neutrophil count (ANC) – Absolute lymphocyte count (ALC) – Platelet count
Coagulation^a	
– Prothrombin time/International Normalized Ratio	– Activated partial thromboplastin time
Chemistry	
– Sodium	– Total bilirubin ^b
– Potassium	– Alkaline phosphatase
– Creatinine	– Lactic acid dehydrogenase (LDH)
– Aspartate aminotransferase (AST)	– Calcium ^a
– Alanine aminotransferase (ALT)	– Amylase, lipase
Urinalysis^a	
Standard Urine Dipstick	
Other Tests	
Thyroid panel ^a	Serology (hepatitis B, hepatitis C) and HCV Viral Load: ^a
– Thyroid stimulating hormone (TSH)	– Hepatitis B: HBsAg, anti-HBc
– Triiodothyronine (T3; total or free)	– Hepatitis C: anti-HCV; HCV RNA PCR, if necessary
– Free thyroxine (T4)	
Pregnancy Test (for women of childbearing potential only)	
– serum (<5 IU/mL) β -hCG at Screening; serum or urine thereafter as clinically indicated	

a. Not performed for subjects who crossover from Arm A to Arm B, except as clinically indicated.

b. Direct bilirubin if Gilbert disease.

Indirect Antiglobulin Test (IAT) results

This test no longer needs to be performed since daratumumab treatment is discontinued.

Blood Type, Rh, and Indirect Antiglobulin Test (IAT) should be done before the first dose of daratumumab. Subject red blood cell (RBC) phenotyping (standard or extended) is an alternative option to the IAT test, if locally required. Either method must be completed prior to first daratumumab infusion.

Daratumumab interferes with the IAT, which is a routine pretransfusion test performed to identify a subject's antibodies to minor antigens so that suitable donor blood can be given for transfusion. Daratumumab does not interfere with ABO/RhD typing. CD38 is expressed at very low levels on erythrocytes. Daratumumab binds to the CD38 on erythrocytes, which results in a positive IAT (Indirect Coombs Test). This positive result masks the detection of antibodies to minor antigens and may prevent or delay blood banks from issuing donor blood for transfusion. This effect occurs during daratumumab treatment and for up to 6 months after treatment ends. Subjects will receive a patient identification wallet card for the study that includes the blood profile (ABO, Rh, and IAT or phenotyping) determined before the first infusion of daratumumab along with information on the IAT interference for healthcare providers/blood banks. Subjects are to carry this card throughout the treatment period and for at least 6 months after treatment ends. Blood banks can eliminate the daratumumab interference with IAT by treating reagent RBCs with dithiothreitol (DTT) (Chapuy 2015, 2016).^{10,9}

Possible methods for blood banks to provide safe RBCs for transfusion to subjects receiving daratumumab include:

- a. Providing ABO/RhD compatible, phenotypically (standard or extended phenotyping) or genotypically matched units
- b. Providing ABO/RhD compatible, K-negative units after ruling out or identifying alloantibodies using DTT-treated reagent RBCs

Uncrossmatched, ABO/RhD compatible RBC units should be administered if transfusion is needed emergently as per local blood bank practice.

Despite daratumumab binding to CD38 on erythrocytes, no indication of clinically significant hemolysis has been observed in daratumumab studies. For additional details, refer to the Daratumumab Investigator's Brochure.

Pulmonary Function Test

Subjects with known or suspected COPD must have a FEV1 test during Screening. Refer to Section 6.2.1.1 of the protocol for details on subjects with higher risk of respiratory complications.

Electrocardiogram:

A 12-lead ECG will be performed at Screening and at End-of-Treatment.

During the collection of ECGs, subjects should be in a quiet setting without distractions (eg, television, cell phones). Subjects should rest in a supine position for at least 5 minutes before ECG collection and should refrain from talking or moving arms or legs. If blood sampling or vital sign measurement is scheduled for the same time point as ECG recording, the procedures should be performed in the following order: ECG(s), vital signs, blood draw.

Clinically significant abnormalities will be recorded as adverse events in the appropriate CRF.

Vital Signs

Temperature, pulse/heart rate, blood pressure will be performed as specified in the Time and Events Schedule ([Table 1](#)). Clinically significant abnormalities will be recorded as adverse events in the appropriate CRF.

Blood pressure and pulse/heart rate measurements will be assessed with a completely automated device. Manual techniques will be used only if an automated device is not available. Blood pressure and pulse/heart rate measurements should be preceded by at least 5 minutes of rest in a quiet setting without distractions (eg, television, cell phones).

Physical Examination and ECOG performance status

A complete physical examination should be performed during the Screening Phase and at crossover eligibility assessment. Thereafter, only a symptom directed physical examination is required. Height will be measured at Screening only; weight will be measured regularly at Screening and preinfusion, as specified in Time and Events schedule. Abnormalities will be recorded in the appropriate section of the CRF. ECOG performance status will be used to evaluate the effect of the disease status on the activities of daily living ([Attachment 3](#)). When scheduled, ECOG assessments should be obtained prior to any other study procedures planned for the same day.

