Hematology (see Section 9.7; performed by local lab)			X		X		X	X	X	X		
Chemistry (see Section 9.7; performed by local lab); see below for amylase, lipase			X		X		X	X	X	X		
HBV/HCV Serology (see Section 9.7; performed by local lab)			X									
Coagulation (see Section 9.7; performed by local lab)			X									
Thyroid function (see Section 9.7; performed by local lab) Amylase, lipase (see Section 9.7; performed by local lab) Screening, C4D1, every third cycle thereafter (ie, C7, C10, C13, etc.) and EOT			X						X	X		
Urinalysis – dipstick			X									
Pregnancy test – serum at Screening within 14 days prior to first study drug administration; serum or urine thereafter if clinically indicated			X									

Table 1: Time and Events Schedule – Safety Run-in, Randomized Arms

Beginning with the implementation of Amendment 7, subjects who continue to derive benefit from atezolizumab treatment, may continue to receive atezolizumab under the supervision of treating investigators in accordance with local regulatory approvals and standard of care guidelines.^{50,51} Data from efficacy and safety evaluations performed according to local regulatory approvals and standard of care guidelines^{50,51} will no longer be collected with the exception of serious adverse events that are to be reported and entered in the Sponsor safety repository.

Assessments	Prescreening (optional)	Screening		Treatment Period (21-day cycles)					EOT (30 +7d after last dose)	Follow-up Period	
				Arm	Cycles 1-3			Cycle 4 and beyond		Pre-PD	Post-PD Survival
					D1 (±3)	D2	D8 (±1)				
Day	Any time prior to start of Screening	-56 to -1	-28 to -1								
Blood group and type assessment and indirect antiglobulin (IAT). ABO, Rh, IAT A wallet card with subject blood type and IAT will be provided					C1D1 predose; Run-in, Arm B						
Study Drug Administration											
For subjects in the Safety Run-in and Arm B, the daratumumab infusion should precede the atezolizumab infusion on Day 1 of each cycle, starting with Cycle 2. Only one agent will be infused at a time. See the SIPPM for additional details. There should be at least 21 days between Day 1 of every dosing cycle (except for daratumumab in Cycles 1-3).											
Atezolizumab				Arm A	X				X		
				Run-in, Arm B	C2/ C3	C1 only			X		
Daratumumab IV (daratumumab will no longer be administered per Amendment 6)				Run-in, Arm B	X		X	X	X		
Ongoing Subject Review											

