- If corticosteroids have been initiated, they must be tapered over ≥ 1 month to ≤ 10 mg/day oral prednisone or equivalent before atezolizumab can be resumed.
- Resumption of atezolizumab may be considered in subjects who are deriving benefit and have fully recovered from the immune-related event. Subjects can be rechallenged with atezolizumab only after approval has been documented by both the investigator (or an appropriate delegate) and the Sponsor.

Table 14: Management Guidelines for Hepatic Events

Event	Management
Hepatic event, Grade 1	
 • Continue atezolizumab. • Monitor LFTs until values resolve to within normal limits.
Hepatic event, Grade 2	
All events:
 
 • Monitor LFTs more frequently until return to baseline values. 
Events of >5 days' duration:
 
 • Withhold atezolizumab for up to 12 weeks after event onset.^a • Initiate treatment with 1–2 mg/kg/day oral prednisone or equivalent. • If event resolves to Grade 1 or better, resume atezolizumab.^b • If event does not resolve to Grade 1 or better while withholding atezolizumab, permanently discontinue atezolizumab and contact
Hepatic event, Grade 3 or 4	
 • Permanently discontinue atezolizumab and contact the Sponsor.^c • Consider subject referral to gastrointestinal specialist for evaluation and liver biopsy to establish etiology of hepatic injury. • Initiate treatment with 1–2 mg/kg/day oral prednisone or equivalent. • If event does not improve within 48 hours after initiating corticosteroids, consider adding an immunosuppressive agent. • If event resolves to Grade 1 or better, taper corticosteroids over ≥ 1 month.

LFT= liver function tests.

- Atezolizumab may be withheld for a longer period of time (ie, > 12 weeks after event onset) to allow for corticosteroids (if initiated) to be reduced to ≤ 10 mg/day oral prednisone or equivalent. The acceptable length of the extended period of time must be agreed upon by the investigator and the Sponsor.
- If corticosteroids have been initiated, they must be tapered over ≥ 1 month to ≤ 10 mg/day oral prednisone or equivalent before atezolizumab can be resumed.

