a. Atezolizumab may be withheld for a longer period of time (ie, >12 weeks after event onset) to allow for corticosteroids (if initiated) to be reduced to ≤10 mg/day oral prednisone or equivalent. The acceptable length of the extended period of time must be agreed upon by the investigator and the Sponsor.

b. If corticosteroids have been initiated, they must be tapered over ≥1 month to ≤10 mg/day oral prednisone or equivalent before atezolizumab can be resumed.

c. Resumption of atezolizumab may be considered in subjects who are deriving benefit and have fully recovered from the immune-related event. Subjects can be rechallenged with atezolizumab only after approval has been documented by both the investigator (or an appropriate delegate) and the Sponsor.

Table 16: Management Guidelines for Endocrine Events

Event	Management
Asymptomatic hypothyroidism	
 • Continue atezolizumab. • Initiate treatment with thyroid replacement hormone. • Monitor TSH weekly.
Symptomatic hypothyroidism	
 • Withhold atezolizumab. • Initiate treatment with thyroid replacement hormone. • Monitor TSH weekly. • Consider subject referral to endocrinologist. • Resume atezolizumab when symptoms are controlled and thyroid function is improving.
Asymptomatic hyperthyroidism	
TSH ≥ 0.1 mU/L and < 0.5 mU/L:
 
 • Continue atezolizumab. • Monitor TSH every 4 weeks. 
TSH < 0.1 mU/L:
 
 • Follow guidelines for symptomatic hyperthyroidism.
Symptomatic hyperthyroidism	
 • Withhold atezolizumab. • Initiate treatment with anti-thyroid drug such as methimazole or carbimazole as needed. • Consider subject referral to endocrinologist. • Resume atezolizumab when symptoms are controlled and thyroid function is improving. • Permanently discontinue atezolizumab and contact the Sponsor for life-threatening immune-related hyperthyroidism.^a

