Symptomatic adrenal insufficiency, Grade 2-4	
 • Withhold atezolizumab for up to 12 weeks after event onset.^b • Refer subject to endocrinologist. • Perform appropriate imaging. • Initiate treatment with 1–2 mg/kg/day IV methylprednisolone or equivalent and convert to 1–2 mg/kg/day oral prednisone or equivalent upon improvement. • If event resolves to Grade 1 or better, resume atezolizumab.^c • If event does not resolve to Grade 1 or better while withholding atezolizumab, permanently discontinue atezolizumab and contact Sponsor.^a
Hyperglycemia, Grade 1 or 2	
 • Continue atezolizumab. • Initiate treatment with insulin if needed. • Monitor for glucose control.
Hyperglycemia, Grade 3 or 4	
 • Withhold atezolizumab. • Initiate treatment with insulin. • Monitor for glucose control. • Resume atezolizumab when symptoms resolve and glucose levels are stable.

Hypophysitis pan-hypopituitarism), Grade 2-3	
 • Withhold atezolizumab for up to 12 weeks after event onset.^b • Refer subject to endocrinologist. • Perform brain MRI (pituitary protocol). • Initiate treatment with 1-2 mg/kg/day IV methylprednisolone or equivalent and convert to 1-2 mg/kg/day oral prednisone or equivalent upon improvement. • If event resolves to Grade 1 or better, resume atezolizumab.^c • If event does not resolve to Grade 1 or better while withholding atezolizumab, permanently discontinue atezolizumab and contact Sponsor.^a • For recurrent hypophysitis, treat as a Grade 4 event.
Hypophysitis pan-hypopituitarism), Grade 4	
 • Permanently discontinue atezolizumab and contact the Sponsor.^a • Refer subject to endocrinologist. • Perform brain MRI (pituitary protocol). • Initiate treatment with 1-2 mg/kg/day IV methylprednisolone or equivalent and convert to 1-2 mg/kg/day oral prednisone or equivalent upon improvement.^b • Initiate hormone replacement therapy if clinically indicated.

TSH=thyroid-stimulating hormone

- a. Resumption of atezolizumab may be considered in subjects who are deriving benefit and have fully recovered from the immune-related event. Subjects can be rechallenged with atezolizumab only after approval has been documented by both the investigator (or an appropriate delegate) and the Sponsor.

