Event	Management
Amylase and/or lipase elevation, Grade 2	
 • Continue atezolizumab. • Monitor amylase and lipase weekly. • For prolonged elevation (eg, > 3 weeks), consider treatment with 10 mg/day oral prednisone or equivalent.
Amylase and/or lipase elevation, Grade 3 or 4	
 • Withhold atezolizumab for up to 12 weeks after event onset.^a • Refer subject to gastrointestinal specialist. • Monitor amylase and lipase every other day. • If no improvement, consider treatment with 1–2 mg/kg/day oral prednisone or equivalent. • If event resolves to Grade 1 or better, resume atezolizumab.^b • If event does not resolve to Grade 1 or better while withholding atezolizumab, permanently discontinue atezolizumab and contact Sponsor.^c • For recurrent events, permanently discontinue atezolizumab and contact the Sponsor.^c
Immune-related pancreatitis, Grade 2 or 3	
 • Withhold atezolizumab for up to 12 weeks after event onset.^a • Refer subject to gastrointestinal specialist. • Initiate treatment with 1–2 mg/kg/day intravenous methylprednisolone or equivalent and convert to 1–2 mg/kg/day oral prednisone or equivalent upon improvement. • If event resolves to Grade 1 or better, resume atezolizumab.^b • If event does not resolve to Grade 1 or better while withholding atezolizumab, permanently discontinue atezolizumab and contact Sponsor.^c • For recurrent events, permanently discontinue atezolizumab and contact the Sponsor.^c
Immune-related pancreatitis, Grade 4	
 • Permanently discontinue atezolizumab and contact the Sponsor.^c • Refer subject to gastrointestinal specialist. • Initiate treatment with 1–2 mg/kg/day intravenous methylprednisolone or equivalent and convert to 1–2 mg/kg/day oral prednisone or equivalent upon improvement. • If event does not improve within 48 hours after initiating corticosteroids, consider adding an immunosuppressive agent. • If event resolves to Grade 1 or better, taper corticosteroids over ≥ 1 month.

a. Atezolizumab may be withheld for a longer period of time (ie, >12 weeks after event onset) to allow for corticosteroids (if initiated) to be reduced to ≤ 10 mg/day oral prednisone or equivalent. The acceptable length of the extended period of time must be agreed upon by the investigator and the Sponsor.

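### No glucose test is scheduled in either arm, although Grade 3-4 hyperglycemia is a rule for withholding atezolizumab

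*Protocol*

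**What the plan says.** Protocol Section 9.7 (Clinical Laboratory Tests) lists the chemistry analytes: sodium, potassium, creatinine, AST, ALT, total bilirubin, alkaline phosphatase, "Lactic acid dehydrogenase (LDH", calcium, amylase and lipase. The Table 1 row reads "Chemistry (see Section 9.7; performed by local lab); see below for amylase, lipase", so it takes its content from Section 9.7. Table 1 has no glucose row, and its urine dipstick is marked at Screening only.

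Table 16 in Attachment 7 has a row headed "Hyperglycemia, Grade 3 or 4". It directs the site to withhold atezolizumab, start insulin and monitor glucose control. The restart condition is "Resume atezolizumab when symptoms resolve and glucose levels are stable". At Grade 1 or 2 atezolizumab continues, with insulin if needed and glucose monitoring.

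Section 6.2.1.4 names type 1 diabetes among the endocrine events associated with atezolizumab, and Attachment 4 lists diabetes mellitus as an anticipated immune-mediated event. Exclusion criterion 6.3 in Section 4.2 lets subjects with controlled type 1 diabetes on stable insulin enrol. Section 6.1.3 gives methylprednisolone before every daratumumab infusion and on the two days after it.

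**The concern.** A dosing rule that depends on a laboratory grade needs a laboratory value. Here glucose monitoring begins only after hyperglycemia has been found, and nothing on the schedule would find it.

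The main exposure is an asymptomatic subject, most plausibly at Grade 3, who keeps receiving atezolizumab when Table 16 says to stop. Missed Grade 1-2 cases matter less, because Table 16 continues atezolizumab there.

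The second problem is comparability. Safety of the combination is a secondary objective in an open-label trial. Steroid premedication was given in one arm only, while detection depended on symptoms or on whether the local panel happened to report glucose. Prompted cases would still reach the adverse event tables in SAP Section 6.1.1, but the shift tables in SAP Section 6.3 would have no scheduled glucose data. The laboratory-abnormality DLT criterion in Table 6 could likewise not be assessed systematically for glucose in the run-in.

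**Working it through.** The plan states no figure on this point, so there is none to reproduce. The check sets the laboratory-driven rules against the schedule, then counts draws and steroid exposure.

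**Rules against schedule.** In the Attachment 7 tables that could be read, four rules act on a laboratory value with no symptom condition in the trigger:

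| Rule | Row or instruction | Test scheduled in Table 1? |
|---|---|---|
| Liver tests, Table 14 | "Monitor LFTs until values resolve to within normal limits" | Yes, chemistry row |
| TSH, Table 16 | "Asymptomatic hypothyroidism" | Yes: Screening, C4D1, every third cycle, End of Treatment |
| Amylase/lipase, Table 18 | "Amylase and/or lipase elevation, Grade 3 or 4" | Yes, same timing as thyroid |
| Glucose, Table 16 | "Hyperglycemia, Grade 3 or 4" | No |

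That is 3 of 4 with a scheduled test. Adrenal and pituitary disorders are also unscheduled, but Section 6.2.1.4 has them worked up on symptoms, and the adrenal row is worded "Symptomatic adrenal insufficiency, Grade 2-4".

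**Scheduled chemistry draws, Cycles 1-3** (Table 1 and the visit schedule in Section 3.1).
- Arm B, weekly visits in all three cycles: 3 + 3 + 3 = 9.
- Arm A, weekly visits in the first two cycles only: 3 + 3 + 1 = 7.
- Each count falls by one if the Cycle 1 Day 1 draw is omitted because Screening was within 7 days.
- Scheduled glucose values: 0 in both arms.

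**Methylprednisolone over the 9 daratumumab infusions of Cycles 1-3** (Section 6.1.3 and Table 8).
- Predose, with the permitted reduction after the second infusion: 100 + 100 + 7 × 60 = 620 mg. Without it: 9 × 100 = 900 mg.
- Postdose: 9 × 2 × 20 = 360 mg.
- Total: 620 + 360 = 980 mg, or 900 + 360 = 1,260 mg.
- Prednisone equivalent (5 mg to 4 mg, Attachment 2): 980 × 5/4 = 1,225 mg; 1,260 × 5/4 = 1,575 mg.
- Steroid days: 9 × 3 = 27 of 63. In Cycle 1, the DLT window: 3 × 3 = 9 of 21.
- Scheduled in Arm A: none.

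**What a predose glucose would have seen.**
- Weekly dosing: the last steroid is on Day 3 and the next infusion on Day 8, a gap of 5 days, or 5 − 3 = 2 days if the 72-hour predose window allowed after Cycle 1 is used.
- Every-3-week dosing, from Cycle 5 Day 1: Day 3 to Day 22 is 19 days, or 19 − 3 = 16 days.

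Scheduled glucose would therefore show sustained hyperglycemia, including new diabetes, but would miss most transient steroid peaks.

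**The case against.** The strongest reply is that the gap is narrow and mostly in the past.

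- **Prompted testing.** Sections 9.1.4 and 9.7 allow extra testing when clinically indicated, toxicity was reviewed before each daratumumab dose (Section 6.1.5), and enrolled diabetics had to be controlled on insulin. This stands for prompted cases. It does not reach an asymptomatic subject with no known diabetes, and the symptom work-up in Section 6.2.1.4 covers thyroid, pituitary and adrenal tests, not glucose.
- **Symptom wording.** The restart line mentions symptoms, so the contrast with the adrenal rule is less clean than it first appears. That is fair for restarting, but the trigger for withholding carries no symptom condition.
- **The 3-of-4 count.** The body of Table 23 (nephritis) was not in the copy reviewed, so the count excludes it. Thyroid, amylase and lipase tests have no on-treatment draw in Cycles 1-3, and the thyroid panel was not routine for crossover subjects. These points weaken the comparison but leave glucose with no scheduled test at all.
- **Size of harm.** The documents give no hyperglycemia rate. The steroid total measures exposure, not missed cases, and predose draws would miss most steroid peaks. All of this stands.
- **Timing.** Enrollment is closed, daratumumab has stopped, the database is locked, and Amendment 7 moves monitoring to local standard of care under the product labels. This stands for data collection. Whether those labels already call for glucose checks cannot be seen from the documents.

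**Conclusion.** The concern holds. None of the 11 chemistry analytes is glucose, no Table 1 visit schedules it in any arm, and a rule that withholds atezolizumab and starts insulin depends on it. That asymptomatic cases can be missed is an inference from the schedule, and their number cannot be estimated. It assumes that some Grade 3 hyperglycemia is silent and that local panels do not uniformly report glucose.

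The arm contrast concerns the trial as designed and conducted. Amendment 6 kept Table 1 and Section 9.7, still without glucose, for subjects continuing atezolizumab (Section 9.2). Since Amendment 7, only diabetes monitoring in subjects still on atezolizumab remains live. The ORR analysis is not affected. This is an inexpensive safety improvement that should be made.

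**What to change.** For the trial as designed, add serum glucose to the chemistry list in Section 9.7. It would be run on the chemistry samples already taken at Screening and at each Table 1 chemistry visit, and included in the descriptive and toxicity-grade shift tables of SAP Section 6.3. Table 16 needs no change. The cost is one analyte on blood already drawn and tested locally, one CRF laboratory field and one SAP table row, with no extra visit or procedure. The downsides are some non-fasting values to interpret and the steroid peaks that predose draws still miss.

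After database lock only one step can be implemented: a line in Section 9.3 reminding sites to check glucose with local predose chemistry for subjects still receiving atezolizumab, with no Sponsor data collection.
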